5.2.2 Safety Analysis Set

The SafAS is defined as those subjects who have received at least one dose of the study vaccines^a.

All subjects will have their safety analyzed as following:

- After each dose, according to the vaccine they actually received at the dose considered
- After any dose, according to the vaccine received at the first dose. In case the second dose received is different, safety data recorded at V04 and V05 will be excluded from this analysis and listed separately.

Safety data recorded for a vaccine received out of the protocol design will be excluded from the analysis (and listed separately).

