***Visit 3 (28 [+7] days after Visit 1) – for previously influenza unvaccinated subjects 6 months to 8 years of age***

**The Investigator or delegate will:**

- 1) Review (for clarity, content, and completeness) and collect the DC1 information with the parent / guardian and clarify with the parent / guardian if required any AEs, medications (see [Section 6.7](#)), or SAE that occurred since V02. If an SAE occurred, follow the instructions in [Section 10](#) for reporting it.

- 2) Conduct a targeted physical examination, if necessary.

- 3) Review temporary and definitive contraindications to vaccination.

- 4) Draw approximately 5 mL of blood sample (The blood sampling should be performed before vaccination). Process the blood sample as specified in the “Management of Samples” section (see [Section 7](#)).

**Note:** If 5 mL of blood sample cannot be drawn, a volume less than 5 mL can be obtained.

**Note:** If the attempt(s) to collect blood is (are) unsuccessful (3 attempts), the parent / guardian should be given the opportunity to bring his / her child to the study site for another attempt within the visit window. If a blood sample cannot be obtained, the reason will be recorded in the blood sampling page of the CRB. In this case, the subject will remain in the study and should be vaccinated after all the attempts to collect blood are complete.

The unblinded qualified study staff member will:

- 5) Call the IRT to obtain a unique dose number
- 6) Administer the appropriate vaccine intramuscularly into the anterolateral muscle of the thigh or the deltoid muscle of the upper arm, as appropriate (the vaccine must be administered on the side opposite to that of the blood sampling).
- 7) Record the injection site / side / route / dose number in the source documents and affix the detachable corresponding label in the source document.

The Investigator or delegate will:

- 8) Keep the subject under medical surveillance for at least 30 minutes after the injection and report the occurrence or non-occurrence of any AE in the source documents.
- 9) Give the subject / parent / guardian the DC2 to record any injection site reactions and systemic AEs, together with instructions for its completion, including explanations on the definition and use of intensity scales for collection of AEs.
- 10) Remind the subject / parent / guardian to bring back the DC2 when they return for V04.

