- 11) Remind the subject / parent / guardian to promptly notify the site in case of an SAE that may occur at any time during the study.
- 12) Complete the relevant CRB forms for this visit.

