#### 9.1.3.1 Immediate Post-vaccination Observation Period

Subjects will be kept under observation for 30 minutes after each vaccination to ensure their safety. The post-vaccination observation should be documented in the source document. Any AE that occurs during this period will be noted on the source document and recorded in the CRB, as follows:

- Unsolicited systemic AEs will be recorded as immediate AEs in the CRB (presence marked as "yes" and details collected).
- Solicited and unsolicited injection site reactions and solicited systemic reactions will be recorded in the CRB in the same way as any reactions starting on the day of vaccination.

- SAEs will be recorded in the CRB and reported to the Sponsor in the same way as any other SAEs, according to the procedures described in [Section 10](#).

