4.4.1.3.2 Time of Onset

Time of onset will be computed using the same methodology as for unsolicited non-serious AEs described in [Section 4.4.1.2.4](#).

SAEs will be analyzed throughout the study using the following periods:

- During post-Dose period (within 28 days after any injection)
- During the whole study (ie, all SAEs occurred during the study)

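### When dose 2 is a different vaccine, excluding only V04 and V05 data leaves immediate events at V03, and SAEs/AESIs first recorded after V05, under the dose 1 vaccine in the after-any-dose safety analysis

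*SAP*

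**What the plan says.** SAP 5.2.2 and Protocol 12.2.2 set out two safety analyses in identical terms. One is by dose: "After each dose, according to the vaccine they actually received at the dose considered". The other is cumulative: "After any dose, according to the vaccine received at the first dose". The cumulative rule has one exception for a mismatched second dose: "In case the second dose received is different, safety data recorded at V04 and V05 will be excluded from this analysis and listed separately". A further sentence follows: "Safety data recorded for a vaccine received out of the protocol design will be excluded from the analysis (and listed separately". Neither document defines what that last sentence covers, or what makes a second dose different.

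SAP 5.1.1.2 makes both the after-any and the after-each presentation part of the main safety analyses. For SAEs, SAP 4.4.1.3.2 gives two periods: within 28 days of any injection, and "During the whole study (ie, all SAEs occurred during the study".

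**The concern.** The exception is evidently meant to stop events that follow a switched dose from being counted against the first vaccine. It does this by naming the visits at which data are recorded, not by asking whether the event began after dose 2. Those two tests differ at both ends of the period. Dose 2 is injected at V03, so some post-dose-2 data are V03 data. SAE and AESI collection runs to a telephone contact about six months after the last vaccination, which is neither V04 nor V05.

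The result would be a cumulative safety table that charges an event to a product the child had not most recently received. A child switched from QIV-SD to QIV-HD would add a post-QIV-HD event to the QIV-SD column, and the opposite switch would do the reverse. A secondary effect is that an event which began before dose 2 but was first reported at V04 or V05 would be dropped.

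**Working it through.** There is no planned figure to reproduce. The check is to trace each kind of record after dose 2 to the place where it is entered, and then apply the V04/V05 wording.

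| Record after dose 2 | Where it is recorded | Removed by the rule? |
|---|---|---|
| Immediate unsolicited systemic AE | V03 forms (Protocol 5.1.4, Visit 3 for unvaccinated subjects, steps 8 and 12; 9.1.3.1) | No |
| SAE during the 30-minute observation | CRB at V03 (same sections) | No |
| Solicited reactions and all injection-site reactions, including those in the 30 minutes | Treated like other day-of-vaccination reactions (9.1.3.1), so through diary card 2; D28-D35 data entered at V04 (5.1.4, Visit 4, step 2) | Yes |
| Other unsolicited AEs to D56 | Diary card 2, reviewed at V04 and collected at V05 | Yes |
| SAE/AESI first recorded after V05 | Memory aid and follow-up call (Table of Study Procedures 3; SAP Table 3.4) | No |

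The first row rests on three statements. At V03 the investigator must "Keep the subject under medical surveillance for at least 30 minutes after the injection and report the occurrence or non-occurrence of any AE" and then "Complete the relevant CRB forms for this visit". Under Protocol 9.1.3.1, "Unsolicited systemic AEs will be recorded as immediate AEs in the CRB". The last row matters because SAEs are also summarised over the whole study.

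**Length of the uncovered SAE/AESI period.** Inputs from Table of Study Procedures 3: V03 at D28; V05 at 28 (+7) days after V03; call at 180 (+14) days after V03.

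- Planned duration: 28 + 180 = 208 days, which agrees with the stated figure.
- Nominal time after V05: 180 - 28 = 152 days; 152/180 = 84%.
- Latest V05, earliest call: 180 - 35 = 145 days; 145/180 = 81%.
- Earliest V05, latest call: 194 - 28 = 166 days; 166/194 = 86%.

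These are days of SAE/AESI follow-up, not a share of safety data. Only SAEs and AESIs are collected in that period.

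**Children to whom the rule could apply.** Inputs from Protocol 12.5.

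- Groups 6 and 8, all two-dose: 60 + 60 = 120.
- Mixed-status Groups 1-5 and 9-11: (40 + 40 + 40 + 90 + 40) + (40 + 40 + 60) = 250 + 140 = 390.
- Planned two-dose children therefore number between 120 and 120 + 390 = 510 of 700.

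The number who actually receive a different second vaccine is not given, so the numerical effect on the tables cannot be computed. As an illustration only, one misassigned event is 1/10 = 10% (Clopper-Pearson 95% CI 0.3% to 44.5%) in a 10-child control arm, or 1/30 = 3.3% (0.1% to 17.2%) in a 30-child arm.

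**The case against.** The strongest reply is that the next sentence of the same section already excludes data for a vaccine outside the protocol design. If a mismatched second dose is such a vaccine, nothing is misattributed. This cannot be ruled out, because the term is undefined. It is the weaker reading, though: it would make the V04/V05 sentence redundant, and it would conflict with analysing each dose by the vaccine actually received.

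A second reply is that the database may handle these events correctly. SAP 4.4.1.2.3 and 4.4.1.3.1 link an event to a vaccination by visit number first and start date second. The documents do not say which visit number a V03 immediate AE or a post-V05 SAE carries. That is a fair limit on any statement about what the programs will do, but it does not repair the wording.

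Two stronger conclusions might be inferred, and neither is supported:

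- **That all reactions just after the wrong dose are charged to the first vaccine.** Solicited and injection-site reactions go through diary card 2 to V04 and are excluded, and these are the bulk of reactogenicity data.
- **That a QIV-HD signal would be masked.** The after-each-dose analysis, also a main analysis, assigns the event to the vaccine actually given. Every SAE is also reported within 24 hours and assessed for causality by the investigator and the sponsor (Protocol 10.1 and 10.4).

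An onset-based rule is not entirely free either. Protocol 9.1.3.3 lists start and stop dates for unsolicited AEs, not clock times, so a date alone cannot place a D28 event before or after the injection. Missing start dates are not imputed (SAP 5.3.1.5). Both points stand, and the fix has to provide for them.

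**Conclusion.** The concern holds in a limited form. On a literal reading of both documents, the after-any-dose analysis keeps two kinds of event under the dose 1 vaccine after a switch: immediate unsolicited systemic AEs (and any SAE) recorded at V03, and SAEs/AESIs first recorded after V05. The second gap spans nominally 152 of 180 days of SAE/AESI follow-up (81% to 86% across the visit windows). It mainly affects the whole-study SAE summary, because V05 is scheduled no earlier than 28 days after dose 2, so an SAE starting after it normally falls outside the 28-day period.

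This is a stated rule that gives the wrong attribution, not a missing detail, so it is worth correcting. The expected impact is small: it needs a dose 2 error and then one of these events in the same child, and all analyses are descriptive. The conclusion assumes that the sentence on vaccines outside the protocol design does not cover a mismatched second dose, and that the words about the visit of recording mean what they say.

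**What to change.** Replace the visit-based cut in SAP 5.2.2 and Protocol 12.2.2 with wording such as:

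*If the second dose is a different vaccine, every event with onset after that dose, including immediate AEs at V03 and SAEs/AESIs up to the 6-month contact, is left out of the after-any-dose analysis and shown in a separate listing. Events with onset before that dose are kept, whichever visit they were recorded at.*

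Add a convention for the unclear cases:

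- Events on the day of dose 2 are assigned by the immediate-AE record, or by the diary card (1 or 2) on which they were reported.
- Events with a missing start date are assigned by the visit collected, as SAP 5.3.1.5 already does.

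Also state whether a mismatched second dose counts as a vaccine outside the protocol design, and whether another QIV-HD dosage counts as different. Simply adding V03 to the list of excluded visits would be wrong, because diary card 1, with the dose 1 data, is reviewed and collected at V03.

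The after-each-dose analysis stays as it is. The cost is a few sentences in each document, one extra derivation and the convention above. No new data need to be collected.

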5.2.3 Populations Used in Analyses

All randomized subjects with data in the CRB will be taken into account in the description of the population (eg, the disposition, the demographic, or baseline characteristics).

The safety analyses will be performed on the SafAS.

The immunogenicity analyses from HAI assay and SN assay will both be performed on the IAS.

5.3 Handling of Missing Data and Outliers

5.3.1 Safety

No replacement will be done. Nevertheless, missing relationship will be considered as related at the time of the statistical analysis. No search for outliers will be performed. In all subject listings, partial and missing data will be clearly indicated as missing.

5.3.1.1 Immediate

For unsolicited non-serious systemic AEs, a missing response to the “Immediate” field is assumed to have occurred after the 30-minute surveillance period and will not be imputed.

For SAEs, missing or partially missing elapsed time from last vaccination recorded if within 24 hours will remain missing and will not be imputed. Such SAEs will not be considered as immediate.

5.3.1.2 Causality

Missing causality (relationship) for unsolicited non-serious AEs and SAEs will be considered at the time of analysis as related to vaccination.

^a for which safety data are scheduled to be collected

5.3.1.3 Measurements

Partially missing temperatures will be handled as described in [Section 4.4.1.1.1](#).

5.3.1.4 Intensity

For solicited reactions, missing intensities will be handled as described in [Section 4.4.1.1.1](#). For unsolicited non-serious AEs, missing intensities will remain missing and will not be imputed.

5.3.1.5 Start Date and Stop Date

Missing or partially missing start dates for unsolicited AEs will remain missing and will not be imputed. If either the start or stop date is missing or partially missing, the time of onset will be considered to be missing. Nevertheless unsolicited AEs with missing time of onset will be included in analyses according to the visit collected.

Missing or partially missing stop dates for AEs (solicited reactions and unsolicited AEs) will remain missing and will not be imputed.

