4.4.1.2.4 Time of Onset

Time of onset is derived from the start date of the unsolicited non-serious AE provided in the clinical database and the date of last vaccination:

- Start date of the unsolicited non-serious AE – date of vaccination.

The time of onset should be considered as missing only if one or both of the dates are missing or partially missing.

The unsolicited non-serious AEs will be analyzed “Within 28 days”, which corresponds to AEs with a time of onset between 0 and 28 days after vaccination or missing. An AE with missing time of onset will be considered to have occurred just after the vaccination indicated by the visit number (See [Section 4.4.1.2.3](#)), so will be included in these tables.

Note: Unsolicited non-serious AE that occurred before vaccination (negative time of onset) or with a time of onset higher than defined above (> 28 days) will not be included in analysis, but will be listed separately.

Time of onset will be displayed as follows:

- D0-D3
- D4-D7
- D8-D14
- $\geq D15$
- Missing

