4.4.1.2.5 Duration

Duration is derived from the start and stop dates of the unsolicited non-serious AE provided in the clinical database:

- Stop date of unsolicited non-serious AE - start date of unsolicited non-serious AE + 1.

The duration should be considered as missing only if one or both of the start and stop dates of the unsolicited non-serious AE is missing or partially missing.

Duration will be displayed by period as following:

- 1-3 days

- 4-7 days
- 8-14 days
- ≥ 15 days
- Missing

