5.1.1.2.1 Safety

Safety endpoints will be analyzed descriptively for subjects in safety analysis set (SafAS). Solicited reactions (solicited injection site and systemic reactions), unsolicited AEs, SAEs, and AESIs will be summarized. The main parameters will be described by single proportions with the 95% CI (Clopper-Pearson method) (9).

- Occurrence, nature (Medical Dictionary for Regulatory Activities [MedDRA] PT), duration, intensity, and relationship to vaccination of any unsolicited systemic AEs reported in the 30 minutes after each vaccination.
- Occurrence, time to onset, number of days of occurrence, intensity, action taken, and whether the reaction led to early termination from the study, of solicited (prelisted in the subject's diary card and CRB) injection site reactions and systemic reactions occurring up to 7 days after each vaccination.
- Occurrence, nature (MedDRA system organ class [SOC] and PT), time to onset, duration, intensity, relationship to vaccination (for systemic AEs only), and whether the event led to early termination from the study, of unsolicited AEs up to 28 days after each vaccination.
- Occurrence, nature (MedDRA SOC and PT), time to onset, seriousness criteria, relationship to vaccination, outcome, and whether the event led to early termination from the study, of SAEs (including AESIs) throughout the study.
- Occurrence, nature (MedDRA PT), time to onset, and relationship to vaccination of AESIs throughout the study.

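### SAP 5.3.1.5 sets time of onset to missing when only the stop date is missing, which contradicts the definition of onset in SAP 4.4.1.2.4

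*SAP*

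**What the plan says.** Three SAP sections deal with incomplete dates for unsolicited AEs.

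- **4.4.1.2.4 (Time of Onset)** subtracts the date of vaccination from the start date of the event. It then says: "The time of onset should be considered as missing only if one or both of the dates are missing or partially missing". The 28-day analysis takes in "AEs with a time of onset between 0 and 28 days after vaccination or missing". It adds: "An AE with missing time of onset will be considered to have occurred just after the vaccination indicated by the visit number". Events with a negative onset, or "with a time of onset higher than defined above (> 28 days) will not be included in analysis, but will be listed separately".
- **4.4.1.2.5 (Duration)** uses the start and stop dates of the event: "The duration should be considered as missing only if one or both of the start and stop dates" are incomplete.
- **5.3.1.5 (Start Date and Stop Date)**, under the heading on missing data, says: "If either the start or stop date is missing or partially missing, the time of onset will be considered to be missing". It keeps such events in the analysis under the visit at which they were collected, and it rules out imputing stop dates.

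For SAEs, 4.4.1.3.2 refers back to the non-serious rule: "Time of onset will be computed using the same methodology as for unsolicited non-serious AEs".

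**The concern.** The condition in 5.3.1.5 is the one that 4.4.1.2.5 sets for duration, applied instead to onset. A missing stop date says nothing about when an event began.

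Time to onset of unsolicited AEs is part of a stated safety endpoint (Protocol 9.1.2, SAP 5.1.1.2.1). Missing stop dates are foreseen: Protocol 9.1.3.3 has them actively sought only for related AEs, and treats an AE with none as ongoing at the end of the study. The events exposed to the conflict would therefore tend to be the unresolved ones and those judged unrelated, not a random subset.

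Two things are at stake if 5.3.1.5 is the rule coded. A known onset is replaced by the Missing category. And because missing-onset events are admitted to the 28-day tables, an event whose known onset lies outside the window would be counted there.

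**Working it through.** The plan gives no figure to reproduce. The check applies both rules to every combination of complete (C) and missing or partial (M) dates, then to example events.

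**Inputs.** Rule A is SAP 4.4.1.2.4: onset = start date − vaccination date, missing only if either of those dates is M. Rule B is SAP 5.3.1.5: onset is missing if the start date or the stop date is M.

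**Date patterns.** Three dates with two states each give 2 × 2 × 2 = 8 patterns.

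| Vaccination | Start | Stop | Rule A | Rule B | Comparison |
|---|---|---|---|---|---|
| C | C | C | onset known | onset known | agree |
| C | C | M | onset known | missing | **conflict** |
| C | M | C | missing | missing | agree |
| C | M | M | missing | missing | agree |
| M | C | C | missing | silent | B does not mention the vaccination date |
| M | C | M | missing | missing | agree |
| M | M | C | missing | missing | agree |
| M | M | M | missing | missing | agree |

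The result is 6 agreements, 1 pattern on which Rule B is silent, and 1 conflict. These are counts of logical cases and say nothing about how often each occurs.

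**Examples of the conflicting pattern.** These are non-serious AEs with vaccination on Day 0 and no stop date. The start days are assumptions chosen for illustration.

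| Start | Onset under Rule A | Handling under Rule A | Handling under Rule B |
|---|---|---|---|
| Day 2 | 2 − 0 = 2 | category D0-D3, in the 28-day tables | category Missing, in the 28-day tables |
| Day 30 | 30 − 0 = 30, above 28 | listed separately | category Missing, in the 28-day tables |
| Day −1 | −1 − 0 = −1, below 0 | listed separately | category Missing, in the 28-day tables |

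**Can the Day 30 case occur?** Yes. Visits 3 and 5 each fall 28 days after a vaccination with a +7-day window, and the diary card collects unsolicited AEs up to the visit. Onsets from Day 29 to Day 28 + 7 = Day 35 can therefore be recorded.

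**Scope.** SAP 4.4.1.3.2 also tabulates SAEs within 28 days after any injection, so that table is exposed if 5.3.1.5 is applied to SAEs. Three results do not depend on the conflict:

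- whole-study SAE totals, which take every SAE whatever its onset;
- onset of solicited reactions, which comes from daily intensities (4.4.1.1.4);
- the early safety review triggers (Protocol 5.1.6), which are a related SAE or more than 10% of subjects with Grade 3 fever.

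**The case against.** The strongest reply is that this is a drafting slip with an obvious resolution. Section 4.4 holds the calculation methods, gives the formula and restricts missing onset explicitly. Several parts of 5.3 refer back to 4.4: 5.3.1.3 for temperatures, 5.3.1.4 for solicited intensities and 5.3.2 for titers. A careful programmer would probably follow 4.4.1.2.4.

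The consequences are also limited. An AE that starts within 28 days is counted in the 28-day tables under either rule, and only its onset category changes. A late onset is recorded mainly in the Day 29 to 35 tail of the visit window. A pre-vaccination onset should be rare, because enrollment and first vaccination happen at the same visit and pre-existing conditions are not reported as AEs unless they worsen. No rate of missing stop dates is given, and no hypothesis is tested.

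Most of this stands as a limit on size. It does not remove the contradiction. The cross-references do not all run one way: 4.4.1.4.4 sends missing causality to 5.3.1.2, so there the missing-data section governs. For onset there is no cross-reference in either direction, and a programmer handling a missing stop date could reasonably follow the section written for that purpose. The pre-vaccination case is rare, but 4.4.1.2.4 itself provides for a negative onset.

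**Conclusion.** The concern holds. 5.3.1.5 and 4.4.1.2.4 cannot both be followed for an unsolicited AE with complete vaccination and start dates and an incomplete stop date, and nothing in the SAP reconciles them. Followed as written, 5.3.1.5 discards known onsets and can move events into the 28-day tables that 4.4.1.2.4 would list separately.

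The number of affected events cannot be derived from the documents. It depends on how many unsolicited AEs end without a complete stop date and on which rule was coded; if that was 4.4.1.2.4, it is zero. The effect is confined to descriptive tables of unsolicited AEs, plus the 28-day SAE table if 5.3.1.5 is applied to SAEs. It should still be corrected, because describing safety is the study's safety objective and two competent programmers could produce different tables from this text.

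**What to change.** In SAP 5.3.1.5, change the condition for a missing onset so that it names the start date or the vaccination date in place of the start or stop date. Then add a sentence such as: *For unsolicited AEs, an incomplete stop date makes only the duration missing (Section 4.4.1.2.5).* This brings 5.3.1.5 into line with the SAP's own formulas for onset and duration, and closes the gap on a missing vaccination date.

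Confirm which rule the derivation program uses. If it is 5.3.1.5, correct it and rerun the onset and 28-day tables.

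The cost is one phrase and one sentence in the SAP, and one line of code if 5.3.1.5 was programmed. No new data are needed.
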